## **6. STUDY ENDPOINTS**

### **Primary Endpoint:**

The proportion of patients in each treatment group with a complete therapeutic cure of onychomycosis of the target toenail assessed at each of the two test-of-cure visits (Day 141 and Day 365).

### **Secondary Endpoints:**

1. The proportion of patients in each treatment group with a complete or almost complete therapeutic cure of onychomycosis of the target toenail assessed at each of the two test-of-cure visits (Day 141 and Day 365).
2. The proportion of patients in each treatment group with a mycological cure of the target toenail assessed at each of the two test-of-cure visits (Day 141 and Day 365).
3. The proportion of patients in each treatment group with a complete clinical cure of the target toenail assessed at each of three test-of-cure visits (Day 141, Day 281 and Day 365).
4. The proportion of patients in each treatment group with a satisfactory clinical cure of the target toenail assessed at each of three test-of-cure visits (Day 141, Day 281 and Day 365).

**Complete therapeutic cure** is defined as both complete clinical and mycological cure of the target toenail

**Almost complete therapeutic cure** is defined as both mycological and satisfactory clinical cure of the target toenail

**Mycological cure** is defined as a negative KOH test **and** a negative fungal culture.

**Complete clinical cure** is defined as 0% nail involvement.

**Satisfactory clinical cure** is defined as  $\leq 5\%$  of the target toenail involvement.

**NOVUM PHARMACEUTICAL RESEARCH SERVICES  
STATISTICAL ANALYSIS PLAN**

**Novexatin 10% topical solution**

**Protocol / Study No. NVXT 1404/71442603**

**7. STUDY POPULATIONS**

**Intent-to-Treat (ITT) Population**

- All randomized patients who applied at least one dose of assigned study product
- Had a positive mycological culture screening (Visit 1)

The primary analyses will be conducted on the ITT population.

Patients who return randomized product bottles with evidence of intentional tampering or unblinding will be excluded from the ITT population and included in the Safety population.

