12. **Adverse Events:** Any adverse events following first dose will be recorded by patient in diary.

13. Schedule Visit 3.

9.5.3 Visit 3: Day 57 ± 4 (1st Treatment completion; the last dose will be on Day 56)

1. **Urine Pregnancy Test:** For women of childbearing potential, a urine pregnancy test will be performed to evaluate pregnancy. Any patient with a positive pregnancy test will not be allowed participation in the study.
2. **Clinical Laboratory Tests:** Blood and urine sample for safety lab tests will be taken. The tests are outlined in Appendix D.
3. **Vital Signs:** BP, HR, RR and body temperature will be recorded.
4. **Collect Study Product Bottles:** Bottles will be inspected for intentional tampering.
5. **Collect/Review Patient Diary:** Collect patient diary and review for concomitant medications, adverse events and compliance with the protocol.
6. Dispense new diary.
7. **Application Site Reactions:** The Investigator will evaluate the patient for local application site reactions and question patient regarding symptoms experienced since the previous visit based on the scale provided in Appendix C.
8. Trimming target nail, if needed.
9. **Investigator Clinical Assessment:** Perform a foot/toenail exam. Record infected toenail count and nail appearance.
10. **Evaluation of Toenail Appearance and Condition:** The investigator and patients will perform a visual assessment and rate target toenail appearance and condition per Appendix A.
11. **Visual Assessment:** The investigator will assess the nail involvement of the “target toenail”.
12. **Planimetry Assessment:** Appropriate photographic documentation will be obtained in accordance with Canfield Scientific Inc. guidelines for the planimetry assessment.
13. Place all records/ documents in patient’s source folder.
14. Schedule Visit 4.

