2. **Collect/Review Patient Diary:** Collect patient diary and review for concomitant medications, adverse events and compliance with the protocol.
3. Dispense new diary.
4. **Vital Signs:** BP, HR, RR and body temperature will be recorded.
5. **Collect Study Product bottles:** Bottles will be inspected for intentional tampering or un-blinding.
6. Trimming target nail, if needed.
7. **Investigator Clinical Assessment:** Perform a foot/toenail exam. Record infected toenail count, target toenail involvement and nail appearance.
8. **Evaluation of Toenail Appearance and Condition:** The investigator and patients will perform a visual assessment and rate target toenail appearance and condition per Appendix A.

A Randomized, Placebo-Controlled, Double-Blind, Parallel-Group, Multi-Site Phase 2b Clinical Study to Assess the Efficacy, Safety and Tolerability of 8-Week Regimens of Novexatin®, 10% Topical Solution (Taro Pharmaceuticals, USA, Inc.) in Patients with Mild to Moderate Onychomycosis

9. **Visual Assessment:** The investigator will assess the nail involvement of the “target toenail”.
10. **Planimetry Assessment:** Appropriate photographic documentation will be obtained in accordance with Canfield Scientific Inc. guidelines for the planimetry assessment.
11. **Application Site Reactions:** The Investigator will evaluate the patient for local application site reactions and question patient regarding symptoms experienced since the previous visit based on the scale provided in Appendix C.
12. Place all records/ documents in patient’s source folder.
13. Schedule Visit 7.

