9.6.9 Collecting Study Product

At Visits 3 and 6 the study product bottles will be collected and inspected for evidence of tampering.

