**Novexatin 10% topical solution**

**Protocol / Study No. NVXT 1404/71442603**

**4. RANDOMIZATION AND BLINDING**

The study product will be packaged and blinded by an independent clinical packaging company. The randomization will be generated in blocks of 3, containing the study products in three configurations:

- A. bottles #1 & 2 – Test and bottles #3 & 4 – Placebo
- B. bottles #1 & 2 – Test and bottles #3 & 4 – Test
- C. bottles #1 & 2 – Placebo and bottles #3 & 4 – Placebo.

Three patients worth of study product bottles 1 & 2 will be packed into a larger box. This larger box will be designated “one block” of study product. The study product bottles 1 & 2 will be blinded, packaged and delivered to the study site in blocks at the beginning of the enrollment. Bottles 3 & 4 will be delivered to the study site before Visit 5 (2nd treatment start).

At each Visit 2 and Visit 5 each patient will receive two 5 ml bottles of study product according to the randomization code. Patients will be randomized to a treatment regimen in a blinded fashion by assigning randomization numbers in ascending sequential order starting with the lowest available randomization number at each site. All patients randomized will be identified by initials, date of birth, and a unique six-digit patient number. The first two-digits will identify the Investigator site where the patient was enrolled and the last four will correspond with the randomization number of study product bottle assigned to the patient. A perforated or two-part label will be attached to each of the small sized boxes of study product supplies. Both pieces of the label will include the following information: Protocol number, randomization number, space for patient’s initials, statement that the study product is for investigational use only, space for dispensing date and the Sponsor’s name. In addition all patients will be provided with written instructions on how to use the study product. One part of the label shall remain attached to the box. The other part will be removed prior to dispensing and attached to the study product log.

The Investigator, staff at the study site, study monitors, and data analysis/management personnel will be blinded to the patient assignment.

At the end of the study, after all the clinical data has been entered and the study database has been locked, a copy of the randomization will be sent to the statistician.

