**Novexatin 10% topical solution**

**Protocol / Study No. NVXT 1404/71442603**

1. Analysis will be performed also including patients without an assessment at Day  $365 \pm 14$ . Patients with missing data at Day  $365 \pm 14$  will be considered therapeutic failures.
2. Analysis will be performed also including patients without an assessment at Day  $365 \pm 14$ . Patients in Group C with missing data at Day  $365 \pm 14$  will be treated as therapeutic successes and patients from the Groups A and B with missing data at Day  $365 \pm 14$  will be treated as therapeutic failures.

Similar sensitivity analyses will be conducted including patients without an assessment at Day  $141 \pm 7$  for the 4th comparison in the hierarchical, conditional-stepwise evaluation scheme.

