**8.7 Changes to the Protocol Defined Statistical Analysis Plan**

The protocol states that the statistical analysis for superiority will be conducted using two-sided Z-Tests and a pooled response rate for the standard error of the difference in proportions for each comparison of interest. The CMH exact test stratified by clinical site is preferred for a multi-site study for which the randomization is intended to be balanced among treatments within each site (i.e., stratified by site), because it accounts for the variability in clinical site whereas the Z-test does not account for site variability in the model. During the analysis, the statistical analysis for superiority will be conducted using a two-sided Cochran-Mantel-Haenszel (CMH) exact test, stratified by clinical site, at the 5% significance level.

The wording in section 8.5 “Methods for Handling Missing Data” was updated to coincide with the ITT definition. The ITT states that patients will be included in the ITT as long as they have received one dose of assigned study product and had a positive mycological culture at Visit 1.

Additional analyses that were not delineated in the protocol were included in section 8.2.3 of the SAP.

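### Patients whose returned bottles show tampering or unblinding are dropped from ITT after randomisation, contrary to the SAP's own restatement of that population; keep them and exclude them only in a supplementary analysis

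*SAP*

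**What the plan says.** SAP 7 sets two conditions for ITT: at least one dose of assigned product, and a positive screening culture. It then states "The primary analyses will be conducted on the ITT population", and adds the exclusion: "Patients who return randomized product bottles with evidence of intentional tampering or unblinding will be excluded from the ITT population". The same sentence keeps the excluded patients in the Safety population. Protocol 10.3.1 carries the identical rule, so the SAP inherited it.

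The trigger comes after randomisation. Protocol 9.6.9 says "At Visits 3 and 6 the study product bottles will be collected and inspected for evidence of tampering". The visit instructions differ slightly: at Visit 3 (Protocol 9.5.3) "Bottles will be inspected for intentional tampering", and at Visit 6 (Protocol 9.5.6) "Bottles will be inspected for intentional tampering or un-blinding". Neither document says what counts as evidence, who decides, or that the decision must be recorded before lock.

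SAP 8.7 restates the population without the exception: "patients will be included in the ITT as long as they have received one dose of assigned study product", together with a positive Visit 1 culture.

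The two sensitivity analyses in SAP 8.2.1 address missing assessments only. Each opens "Analysis will be performed also including patients without an assessment at Day" 365 ± 14. On blinding, SAP 4 says that after database lock "a copy of the randomization will be sent to the statistician".

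**The concern.** A patient who meets both ITT conditions can lose membership because of something done after treatment began. A decision to tamper with a bottle or find out the assignment may depend on how well the nail seems to be responding, or on local irritation. If so, the patients removed are not a random subset, and the comparison no longer rests on randomisation alone.

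What is at stake is the primary comparison. Under the hierarchy in SAP 8.2.1, Group B versus Group C at Day 365 gates every later comparison, so a change in that one p-value across 5% opens or closes the whole sequence. The report would show how many patients were removed, but no planned table would show what their removal did to the cure rates.

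**Working it through.** **1. Who is in ITT.** Take a patient who was randomised, applied one dose, had a positive Visit 1 culture, and returned a tampered bottle.
- SAP 7 and Protocol 10.3.1: excluded.
- SAP 8.7: included, since one dose plus the positive culture is enough.

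The two SAP sections classify the same patient differently.

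**2. Which outputs contain this patient.** Tables V to VII (primary and both sensitivity analyses) and the T14.2 series (secondary endpoints and planimetry-based versions) are all labelled ITT, so the patient is in none of them. The patient is in the Safety outputs, including T14.3.10, which summarises investigator and patient ratings of the target toenail by visit. The exclusion is counted in Table IV and listed with its reason in L16.2.3.

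**3. Timing.** Bottles 3 and 4 are dispensed at Visit 5, Day 281 (Protocol 9.6.8). Tampering with them cannot affect a Day 141 result, yet the rule removes the patient from the Day 141 comparison too.

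**4. The plan's own figure.** Inputs from SAP 5: 49% versus 21%, two-sided 5% pooled Z test, 46 per group. The mean rate is 0.35.
- Null SE = √(2 × 0.35 × 0.65 / 46) = 0.0995; alternative SE = √((0.49 × 0.51 + 0.21 × 0.79) / 46) = 0.0951.
- Power = Φ((0.28 − 1.96 × 0.0995) / 0.0951) = Φ(0.895) = 81.5%, which agrees with the stated figure of over 80%.
- 46 / 0.77 = 59.7, giving 60 per group and 180 in total.

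The stated size reproduces and does not depend on the exclusion rule.

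**5. Effect on false wins.** The documents give no expected number of such patients, so k = 1 to 3 removals from one arm is an assumption. Set the true rate to 21% in both arms with 46 per group, enumerate all pairs of binomial counts, remove k non-cured patients from one arm, and apply the pooled Z test. The expected rate in the affected arm becomes 0.21 × 46 / (46 − k) = 9.66 / (46 − k), where 9.66 is an expected value and not a count.

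| k | Rate in affected arm | False win for active, removed from active | False win for active, removed from placebo |
|---|---|---|---|
| 0 | 21.0% | 2.52% | 2.52% |
| 1 | 9.66/45 = 21.5% | 2.90% | 2.30% |
| 2 | 9.66/44 = 22.0% | 3.35% | 1.98% |
| 3 | 9.66/43 = 22.5% | 3.87% | 1.68% |

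The last column follows by symmetry. With equal sizes and equal true rates, it equals the chance of a false win for placebo when the same number of non-cured patients is removed from active.

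**6. A borderline result.** z = (p₁ − p₂) / √(p(1 − p)(1/n₁ + 1/n₂)), with p the pooled rate.
- 18/46 versus 10/46: p = 28/92 = 0.304, difference 0.174, SE 0.0959, z = 1.81, p-value 0.070.
- Two non-cured active patients removed, 18/44 versus 10/46: p = 28/90 = 0.311, difference 0.192, SE 0.0976, z = 1.96, p-value 0.0496.

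These figures use the protocol's Z test. The SAP's exact CMH test stratified by site would give somewhat different values, which cannot be computed without site counts.

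**The case against.** The rule has a rationale. Complete cure rests partly on the investigator's visual judgement of nail involvement and on an on-site KOH test. Protocol 9.4.4 asks patients not to discuss the bottle's appearance with staff, so it takes leakage to the assessor seriously. An outcome rated after unblinding may itself be biased. A reader might infer that the exclusion serves no purpose; the documents do not support that. They also do not show that it must act on the primary analysis, because a supplementary analysis meets the same concern.

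The rule is prespecified, worded alike for all groups, and shielded from selection by arm because the codes are held until lock. Opportunity is limited: labels are blacked out, products are described as indistinguishable, and the code portion of the label stays at the site. All of this stands, and it makes deliberate selection unlikely. It does not remove the possibility that the behaviour itself depends on perceived response, which a blinded decision would not correct.

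SAP 8.7 may be only a shortened paraphrase of the definition. Even so, the two sections need to agree.

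Three further inferences go too far. One is that no planned analysis of any kind includes these patients; the Safety outputs do. Another is that the rule favours the active arm; nothing in the documents gives a direction. The third is that type I error could be heavily inflated. Removing three cured placebo patients would raise the false-win chance to 12.2%, but nothing suggests that tampering would concentrate among cured placebo patients.

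Finally, a few exclusions are minor beside an observed-case primary analysis with 23% drop-out planned. That is fair and limits the priority of the point.

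**Conclusion.** The point holds as a cheap improvement. A stated rule removes randomised, dosed, culture-positive patients from every planned cure-rate analysis on the basis of later behaviour, disagrees with SAP 8.7, and reaches back to Day 141 results recorded before the second set of bottles was dispensed.

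Bias is possible, not shown; it could run either way and is probably small. The sizes in steps 5 and 6 of the working rest on four assumptions: 1 to 3 removals, all from one arm, all non-cured, and the pooled Z test. Under them the false-win chance for active moves by at most about 1.4 percentage points (3.87 − 2.52), and in the opposite direction if the removals come from placebo. The practical exposure is a result close to 5% in the comparison that gates the hierarchy.

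**What to change.** Delete the exclusion sentence in Protocol 10.3.1 and SAP 7, so that both agree with SAP 8.7. Analyse these patients in ITT as randomised and record them in the protocol deviation listing (L16.2.2), which already exists. Add one supplementary analysis that repeats the primary analysis without them. State what counts as evidence of tampering or unblinding, use the same wording for the Visit 3 and Visit 6 inspections, and have the patients identified and recorded before database lock while the team is blinded.

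The cost is a one-sentence deletion in each document, a short definition, and one extra table. No additional patients are needed: the calculation stays at 46 per group with 81.5% power. The downside is that the primary set may contain a few outcomes rated after possible unblinding, which the supplementary analysis is there to examine.

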**Safety Population**

All patients who were randomized and received study product will be included in the Safety population.

**8. STATISTICAL ANALYSIS METHODS**

If not otherwise specified, statistical significance is defined as  $p < 0.05$  and is two-tailed. Data will be summarized with respect to demographic and baseline characteristics and safety variables.

For categorical variables, the number and percent of each category within a parameter will be calculated for non-missing data. For continuous variables, statistics will include n, mean, standard deviation, median, minimum and maximum values.

All statistical analyses will be conducted using SAS®, Version 9.4 or higher. Datasets will be prepared using headings from Clinical Data Interchange Consortium (CDISC) Study Data Tabulation Model (SDTM) implementation for human clinical trials and ADaM (Analysis Dataset Model).

**8.1 Baseline Characteristics**

**8.1.1 Patient Disposition**

The patient disposition information will be summarized by treatment group. The number of patients randomized, treated with study medication will be tabulated by treatment group. In addition, completion status and primary reason for withdrawal will be summarized by treatment group.

**NOVUM PHARMACEUTICAL RESEARCH SERVICES  
STATISTICAL ANALYSIS PLAN**

**Novexatin 10% topical solution**

**Protocol / Study No. NVXT 1404/71442603**

**8.1.2 Demographic and Other Baseline Characteristics**

Baseline comparability of all treatment groups will be evaluated separately in the ITT and Safety populations.

The following baseline demographics (determined from their initial study visit) will be evaluated:

- Age (years)
- Gender (male/female)
- Ethnicity (Hispanic/non-Hispanic)
- Race (White, Black/African American, Native Hawaiian or Other Pacific Islander, Asian, American Indian or Alaska Native, Other)

Summary tables by treatment group will be presented. Continuous variables will be summarized using descriptive statistics (n, mean, standard deviation, median, minimum, maximum).

Categorical variables will be summarized using frequencies and percentage.

Baseline comparability of the treatments will be presented using Chi-square test for the categorical variables, and Analysis of Variance for the continuous variables.

All data will be listed by treatment group and patient.

**8.1.3 Medical History**

At Visit 1, patients will be questioned about medical history, including acute and chronic medical history and medical history relevant to their onychomycosis.

Medical history data will be listed by treatment group and patient.

**8.1.4 Concomitant Medications**

At Visit 1, patients will be questioned about current and concomitant medication use over the previous 6 months. At all other clinic visits, patients will be questioned about ongoing or new concomitant medication use.

All prior and concomitant medications taken since screening until the end of the study will be listed by treatment group and patient.

**8.2 Efficacy Analyses**

**8.2.1 Efficacy Analyses on Primary and Secondary Endpoints**

The ITT population will be used to evaluate the efficacy of Novexatin® 10% topical solution for

**NOVUM PHARMACEUTICAL RESEARCH SERVICES**  
**STATISTICAL ANALYSIS PLAN**

**Novexatin 10% topical solution**

**Protocol / Study No. NVXT 1404/71442603**

the 8-week treatment regimens in Groups A, B and C.

Descriptive statistics will be summarized for the primary and secondary endpoints (including planimetry data) by study group. As this is a multi-centered study, results may also be presented by study site.

In order to preserve an overall type-I error (alpha) of 5% for evaluation of complete and almost complete therapeutic cure, complete and satisfactory clinical cure and mycologic cure, a hierarchical evaluation scheme will be employed for the primary and secondary endpoints. The four comparisons of interest for the primary endpoint and the secondary endpoints -1 and -2 are:

1. Group B versus Group C – at the test-of-cure visit at Day 365
2. Group A versus Group C – at the test-of-cure visit at Day 365
3. Group B versus Group A – at the test-of-cure visit at Day 365
4. (Group A + Group B) versus Group C – at the test-of-cure visit at day 141

The five comparisons of interest for the secondary endpoints -3 and -4 are:

1. Group B versus Group C – at the test-of-cure visit at Day 365
2. Group A versus Group C – at the test-of-cure visit at Day 365
3. Group B versus Group A – at the test-of-cure visit at Day 365
4. (Group A + Group B) versus Group C – at the test-of-cure visit at Day 281
5. (Group A + Group B) versus Group C – at the test-of-cure visit at Day 141

Statistical testing will begin with comparison 1. If statistical significance is attained with comparison 1 ( $p < 0.05$ ), then a claim of superiority for comparison 1 can be made and the next comparison in the hierarchical evaluation scheme can be tested for statistical significance. If statistical significance is not attained for comparison 1 ( $p \geq 0.05$ ), then testing of all subsequent comparisons is stopped. The hierarchical, conditional-stepwise evaluation scheme allows for each comparison to be evaluated at the 5% level, while preserving an overall type I error rate of no more than 5%. For the proportion of patients in each treatment group with a complete and almost complete therapeutic cure, complete and satisfactory clinical cure and mycological cure of onychomycosis of the target toenail, the statistical analysis for superiority will be conducted using a two-sided Cochran-Mantel-Haenszel (CMH) exact test, stratified by clinical site, at the 5% significance level. The primary and secondary analyses will be performed using an observed case (OC) analysis in the ITT population. Patients discontinued because of lack of treatment effect will be included in the primary analysis as treatment failures.

The following two sensitivity analyses will also be performed on the primary efficacy endpoint in the hierarchical, conditional-stepwise evaluation scheme:

**NOVUM PHARMACEUTICAL RESEARCH SERVICES  
STATISTICAL ANALYSIS PLAN**

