10.6 Efficacy Analyses

The ITT population will be used to evaluate the efficacy of Novexatin® 10% topical solution for the 8-week treatment regimens in Groups A, B and C.

Descriptive statistics will be summarized for the primary and secondary endpoints (including planimetry data) by study group. As this is a multi-centered study, results may also be presented by study site.

In order to preserve an overall type-I error (alpha) of 5% for evaluation of complete and almost complete therapeutic cure, complete and satisfactory clinical cure and mycologic cure, a hierarchical evaluation scheme will be employed for the primary and secondary endpoints. The four comparisons of interest for the primary endpoint and the secondary endpoints -1 and -2 are:

1. Group B versus Group C – at the test-of-cure visit at Day 365
2. Group A versus Group C – at the test-of-cure visit at Day 365
3. Group B versus Group A – at the test-of-cure visit at Day 365
4. (Group A + Group B) versus Group C – at the test-of-cure visit at day 141

The five comparisons of interest for the secondary endpoints -3 and -4 are:

1. Group B versus Group C – at the test-of-cure visit at Day 365
2. Group A versus Group C – at the test-of-cure visit at Day 365
3. Group B versus Group A – at the test-of-cure visit at Day 365
4. (Group A + Group B) versus Group C – at the test-of-cure visit at Day 281
5. (Group A + Group B) versus Group C – at the test-of-cure visit at Day 141

A Randomized, Placebo-Controlled, Double-Blind, Parallel-Group, Multi-Site Phase 2b Clinical Study to Assess the Efficacy, Safety and Tolerability of 8-Week Regimens of Novexatin®, 10% Topical Solution (Taro Pharmaceuticals, USA, Inc.) in Patients with Mild to Moderate Onychomycosis

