Statistical testing will begin with comparison 1. If statistical significance is attained with comparison 1 ($p < 0.05$), then a claim of superiority for comparison 1 can be made and the next comparison in the hierarchical evaluation scheme can be tested for statistical significance. If statistical significance is not attained for comparison 1 ($p \geq 0.05$), then testing of all subsequent comparisons is stopped. The hierarchical, conditional-stepwise evaluation scheme allows for each comparison to be evaluated at the 5% level, while preserving an overall type I error rate of no more than 5%. For the proportion of patients in each treatment group with a complete and almost complete therapeutic cure, complete and satisfactory clinical cure and mycological cure of onychomycosis of the target toenail, the statistical analysis for superiority will be conducted using two-sided Z-Tests and a pooled response rate for the standard error of the difference in proportions for each comparison of interest. The primary and secondary analyses will be performed using an observed case (OC) analysis in the ITT population. Patients discontinued because of lack of treatment effect will be included in the primary analysis as treatment failures.

The following two sensitivity analyses will also be performed on the primary efficacy endpoint in the hierarchical, conditional-stepwise evaluation scheme:

1. Analysis will be performed also including patients without an assessment at Day 365 \pm 14. Patients with missing data at Day 365 \pm 14 will be considered therapeutic failures.
2. Analysis will be performed also including patients without an assessment at Day 365 \pm 14. Patients in Group C with missing data at Day 365 \pm 14 will be treated as therapeutic successes and patients from the Groups A and B with missing data at Day 365 \pm 14 will be treated as therapeutic failures.

Similar sensitivity analyses will be conducted including patients without an assessment at Day 141 \pm 7 for the 4th comparison in the hierarchical, conditional-stepwise evaluation scheme.

Efficacy results will be used to calculate the sample size for the Phase 3 studies.

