#### **8.2.3 Additional Analyses**

In addition to the efficacy statistical analyses specified in the protocol, the analyses described in Section 8.2.1 above, including sensitivity analyses, will also be performed using the following endpoints:

1. Primary endpoint (complete therapeutic cure) with Canfield's evaluation for % toenail involvement.
2. Secondary endpoint #1 (complete or almost complete therapeutic cure) with Canfield's evaluation for % toenail involvement for complete cure in addition to the current evaluation for almost complete cure by Canfield's evaluation.
3. Secondary endpoint #3 (complete clinical cure) with Canfield's evaluation for % toenail involvement for complete cure.

Patients will only be included in analyses 1, 2 and 3 above if they meet inclusion criterion #6 (Mild to moderate severity at Visit 1 as defined by Investigator's estimation of approximately

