**8.4 Multiple Comparisons**

No multiple comparison adjustment will be made in this study other than the pre-defined hierarchical testing for the primary and secondary endpoints.

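### The plan claims an overall type I error of at most 5% over five cure endpoints, but its hierarchy orders only the group comparisons within each endpoint

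*SAP*

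**What the plan says.** The promise covers all five cure endpoints. SAP 8.2.1 opens with "In order to preserve an overall type-I error (alpha) of 5% for evaluation of complete and almost complete therapeutic cure" and goes on to name complete and satisfactory clinical cure and mycological cure. Protocol 10.6 (Efficacy Analyses) states that "a hierarchical evaluation scheme will be employed for the primary and secondary endpoints", and the synopsis says the same.

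Two numbered lists follow. The first is introduced by "The four comparisons of interest for the primary endpoint and the secondary endpoints -1 and -2 are": B vs C, A vs C and B vs A at Day 365, then A+B vs C at Day 141. The second list, for secondary endpoints 3 and 4, starts again at 1 and inserts A+B vs C at Day 281. Testing begins with comparison 1 and stops if that comparison fails. The SAP concludes that this allows "each comparison to be evaluated at the 5% level, while preserving an overall type I error rate of no more than 5" per cent. Protocol 10.6 has the same clause ("while preserving an overall type I error rate of no more than 5" per cent).

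Three other places matter:
- SAP 8.4: "No multiple comparison adjustment will be made in this study other than the pre-defined hierarchical testing for the primary and secondary endpoints".
- SAP 8.7 replaces the protocol's pooled Z test: "During the analysis, the statistical analysis for superiority will be conducted using a two-sided Cochran-Mantel-Haenszel (CMH) exact test, stratified by clinical site".
- SAP 8.2.3 extends the scheme to Canfield-based versions of the primary and of secondary endpoints 1 and 3: "the analyses described in Section 8.2.1 above, including sensitivity analyses, will also be performed using the following endpoints". It does not say whether these fall under the 5% statement.

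**The concern.** A fixed sequence protects only the hypotheses it puts in order. Here the ordered items are contrasts between groups. Comparison 1 (B vs C at Day 365) exists five times, once per endpoint, and nothing says which is tested first or what a failure on one endpoint means for the next. The instruction to stop later comparisons therefore has no defined meaning across endpoints, and no alpha is split between them.

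As written, B vs C could fail on complete therapeutic cure and a superiority claim could still be made on, say, mycological cure, with the documents citing a 5% overall guarantee that the procedure does not have. The primary endpoint itself is not at risk.

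**Working it through.** **Inputs from the documents.** Five endpoints (SAP 6). Lists of 4, 4, 4, 5 and 5 comparisons, so 3×4 + 2×5 = 22 tests (SAP 8.2.1). Each test is two-sided at 5%. Cure is planned at 49% on active and 21% on placebo, with 46 per group and 60 per group after 23% drop-out (SAP 5).

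**Planning figures.** With the pooled Z test at 46 per group, the mean rate is 0.35. The null SE is √(2×0.35×0.65/46) = 0.0995 and the alternative SE is √((0.49×0.51 + 0.21×0.79)/46) = 0.0951. Power is Φ((0.28 − 1.96×0.0995)/0.0951) = Φ(0.895) = 81.5%, and 46/0.77 = 59.7, so 60 per group and 180 in all. The plan's figures reproduce, and 46 is the right base for the error calculation.

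**Within one endpoint.** If each step is tested only after the previous one succeeds, a false claim requires rejection at the first true null in the list, which has probability at most 5%. The table footnotes apply this stop at every step. The plan's figure therefore holds for one list.

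**Across five lists, without a model.** The upper bound is 5×5% = 25%. If the endpoints were independent the rate would be 1 − 0.95⁵ = 22.6%. Counting the three Canfield repeats as independent too, it would be 1 − 0.95⁸ = 33.7%. The endpoints are nested, so the real values are lower and have to be simulated.

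**Simulation.** Each patient has three correlated latent normal variables: mycology, 0% involvement by the investigator, and Canfield involvement ≤5% (protocol 9.6.13 uses the image-analysis value for satisfactory cure). The five endpoints are built from these by their definitions. The documents give no secondary-endpoint rates, correlations or site numbers, so these are assumed:
- mycological cure 25–50%
- complete clinical cure 22–40%
- Canfield ≤5% involvement 25–50%
- resulting primary rate 19–22%, near the planned placebo 21%
- latent correlations 0 to 0.97
- 6 to 10 equal sites.

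Ten scenarios were run at 46 per group: five core scenarios with 6 and with 10 sites (20,000 trials each), and five more with 8 sites, four of them with more extreme correlations (12,000 trials each). Only the latter five were run at 60 per group. Both tests used the same data. The exact CMH test was two-sided by point probability.

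| No true effect, B vs C, Day 365 | Exact CMH | Pooled Z |
|---|---|---|
| One test alone, 46 per group | 2.5–3.2% | 4.3–5.4% |
| At least one false result over five endpoints, 46 per group | 6.5–11.7% | 10.8–18.3% |
| Same, favouring active only (reference 2.5%) | 3.3–5.8% | 5.4–9.3% |
| False secondary result, primary not significant | 3.9–8.9% | 5.9–13.0% |
| At least one, with a primary-first gate | 2.5–3.0% | 4.6–5.3% |
| At least one, 60 per group | 7.2–13.6% | 11.3–19.9% |

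The lowest CMH value is well clear of 5%: its simulation standard error is √(0.065×0.935/12,000) = 0.2 percentage points.

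**Check with a simpler model.** Two latent variables, no sites and 46 per group gave 12.9–18.0% with the Z test and 6.6–9.8% with Fisher's exact test. With three arms, the three Day 365 comparisons and the Z test, separate chains gave 15.9% with no effect anywhere and 15.5% with B effective and A equal to C. One ordered chain over the same 15 tests gave 5.1% and 4.95%, which is 5% within simulation error.

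**The case against.** The strongest reply is that the plan can be read as one scheme, primary first. It speaks of a single hierarchy for primary and secondary endpoints, numbers the secondaries 1 to 4, and stops all later comparisons after a failure. The table shells do not settle the matter. Table V stops after A vs C and the secondary shells restart with a B vs C p-value, but the values are placeholders and SAP 9 says the shells may not reflect every aspect of the study. It stands that separate chains are not proved to be the intention. The reading still fails to rescue the claim, because no endpoint order is written, and an unwritten order cannot support an error-rate guarantee.

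Several objections on size carry weight:
- SAP 8.7 makes the exact CMH test the operative one, so the Z column describes the protocol's superseded method.
- Counting only false results in favour of active, the CMH rate is 3.3–5.8%, close to 5%. But SAP 8 defines significance as two-tailed, so the like-for-like reference for one direction is 2.5%.
- At much lower cure rates (mycology 12%, complete clinical 3%, ≤5% involvement 6%), the CMH rate over five endpoints falls to about 3%. That reflects the conservatism of an exact test with rare events, far from the planned 21%, and gives no guarantee.

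This is also a Phase 2b trial whose results will size Phase 3, and SAP 8.2.3 presents the Canfield tests as additional to the protocol. Both points limit the consequences. Neither makes the overall 5% statement correct.

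**Conclusion.** The concern holds. The documents state an overall error rate that the written procedure does not deliver: control is at 5% per endpoint list, with the primary list intact. At planning-type rates and 46 per group, the chance of at least one false B vs C result at Day 365 is 6.5–11.7% with the SAP's test, and the chance of a false secondary result beside a non-significant primary is 3.9–8.9%. These sizes depend on the assumed marginal rates, correlations and site numbers. The missing order or gate does not. The exposure is limited to claims on secondary endpoints and, as a labelling matter, the Canfield repeats. It should be fixed, but it does not threaten the primary conclusion.

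**What to change.** Choose one of two.

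(a) Write one endpoint order with a gate: the primary list first, then secondary endpoints 1, 2, 3 and 4, stopping at the first p ≥ 0.05. Every later p-value and all the Canfield repeats in SAP 8.2.3 are then labelled nominal.

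(b) Remove the overall claim, state that error is controlled at 5% for the primary endpoint (or for each endpoint separately), and label the secondary and Canfield p-values nominal.

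Option (b) is the more practical. Under (a), B vs A is third in the primary list and both regimens are planned at 49%. If that is true, this step passes at most 5% of the time, so the secondary endpoints would almost never be formally tested.

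The order of group comparisons can stay under either option. The change is to wording: protocol synopsis and 10.6, SAP 8.2.1, 8.2.3 and 8.4, and the table footnotes, with an entry in SAP 8.7, which already records the change of test. A protocol revision goes through the amendment and IRB route in protocol 11.2.3. No data, test or sample size changes. The price is that some or all secondary p-values become descriptive.
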